### **6.3.Secondary endpoints**

- Change in SARS-CoV-2 viral load from baseline (day -1 or day 1 before administration of the study drug) measured at days , 4, 7, 15 and 31.
- Time until the detection of COVID-19 by PCR obtained from nasopharyngeal exudate or sample from the lower respiratory tract compared to baseline (day -2 or -1 or day 1 before administration of the study drug).
- Mortality at 7, 15 and 31 days.
- Percentage of patients requiring invasive mechanical ventilation and/or ICU admission at 7, 15 and 31 days.
- Percentage of patients requiring non-invasive mechanical ventilation at 7, 15 and 31 days.
- Percentage of patients requiring oxygen therapy at 7, 15 and 31 days.
- The recommended dose level will be selected after the joint evaluation of the safety and efficacy data obtained in this study between the sponsor and the Spanish Agency of Medicines and Medical Devices.

## **7. SCREENING OF PATIENTS**

When a patient is considered eligible to participate in the study, they will be offered to participate in it and receive the Patient Information Leaflet along with all additional information required to obtain informed consent.

### **7.1. Inclusion criteria**

1. Patient who agrees to participate in the study by signing the informed consent.
2. Men and women (non-pregnant) aged  $\geq 18$  years.
3. PCR-confirmed COVID-19 infection obtained from nasopharyngeal exudate or sample from the lower respiratory tract.
4. Patients who require hospitalisation for COVID-19
5. Onset of symptoms no later than 10 days prior to study inclusion.
6. Men and women with reproductive capacity must agree to use highly effective contraceptive methods (diaphragm plus spermicide or male condom plus spermicide, oral contraceptive combined with a second method of contraceptive implant, injectable contraceptive, permanent intrauterine device, sexual abstinence or vasectomy) during their participation in the study and in the 6 months following the last administration of plitidepsin.
7. In addition, women participating in the study with reproductive capacity must have a negative pregnancy test at enrolment.

### **7.2. Exclusion criteria**

1. Patients participating in another clinical trial for COVID-19 infection.
2. Patients receiving treatment with antivirals, interleukin-6 receptor inhibitors and immunomodulatory drugs for COVID-19.
3. Patients who are receiving treatment with chloroquine and derivatives.
4. Evidence of multi-organ failure.
5. Patients requiring support with mechanical ventilation (invasive or non-invasive) at the time of inclusion.
6. D-dimer  $> 4 \times$  LSN.
7. Hb  $< 9$  g/dl.
8. Neutrophils  $< 1000/\text{mm}^3$ .
9. Platelets  $< 100,000/\text{mm}^3$ .
10. Lymphopenia  $< 800/\mu\text{l}$ .
11. GOT / GPT  $> 3 \times$  ULN.
12. Bilirubin  $> 1 \times$  ULN.
13. CPK  $> 2.5 \times$  ULN.

14. Creatinine clearance <30 ml/min.
15. Troponin elevation > 1.5 x ULN.
16. Clinically relevant heart disease (NYHA > 2).
17. Clinically relevant arrhythmia or previous history/presence of prolonged QT-QTc interval  $\geq$  450 ms.
18. Pre-existing neuropathies of any type  $\geq$  grade 2.
19. Hypersensitivity to the active substance or to any of the excipients (macrogolglycerol ricinoleate and ethanol)
20. Patients who require or are being treated with strong CYP3A4 inhibitors and inducers (See annex 5).
21. Patients who for any reason should not be included in the study according to the evaluation of the research team.

### **7.3. Randomisation procedures**

Patients will be randomised, provided patients are included at more than one dose level (arm), in a 1:1 or 1:1:1 ratio as appropriate, once the investigator has confirmed that they meet the selection criteria and the patient has given informed consent.

During the extension period, patients will be randomised in a 1:1:1 ratio as appropriate to each dose level (arm).

The randomisation will be done in blocks.

Randomisation will be done through registration in the study's eCRF. The system will assign a unique randomisation number for each patient. This number should be included in all study documents related to the patient.

### **7.4. Masking procedures**

Not applicable.

## **8. WITHDRAWAL AND DISCONTINUATION CRITERIA**

### **8.1. Reason for withdrawal**

Patients will be excluded or withdrawn from the study for any of the following reasons:

- Withdrawal of consent by the patient.
- Administration of treatments not allowed in the protocol.

All cases of a patient's withdrawal from the study must be documented in the Case Report Form.

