### **8.2. Management of withdrawals**

Patients who receive at least one dose of plitidepsin and withdraw from the study will be followed for at least 28 days after administration of the last dose of plitidepsin to follow up on possible open adverse events at withdrawal.

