### **8.3. Replacement of subjects and reserve subjects**

Patients who sign the study consent and are not randomised will be replaced.

Patients who discontinue study treatment before the end of the three proposed administrations for reasons other than  $\geq$  grade 3 adverse events will be replaced.

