### **9.7.Prohibited drugs**

Concomitant administration of interleukin-6 receptor inhibitors and immunomodulatory drugs is not permitted.

Concomitant use of chloroquine and derivatives is not permitted.

Patients may receive other pharmacological treatments for COVID-19 at the discretion of the investigator after 24 hours from the administration of the last dose of plitidepsin.

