3 GENERAL PRINCIPLES

Planned analyses in this document will be carried out once the database is declared cleaned, closed and approved by Pharma Mar according to the premises described in the Data Management Plan version 2.0 approved on 09 June 2020.

Statistical analyses will be performed using SAS software version 9.4 and R. The results of the analyses will be presented in editable format (i.e rtf).

The data will be provided with one decimal place in general. In those cases where greater precision is required, as many decimal places as necessary will be provided.

Before to perform the analyses, the following activities will be performed:

Codification/revision and approval of the following terms:

- Adverse events /procedures according to MedDRA dictionary (latest version available).
- Medication according to the WhoDrug dictionary (latest version available).
- Reconciliation of serious adverse events in the study between the clinical database and the Pharmacovigilance database and resolution of all discrepancies.

Analysis will be done separately for each arm and the total population.

Continuous variables will be presented through the mean, median, standard deviation, range, Q1, Q3 and categorical variables will be presented through the distribution of frequencies and percentages; missing values will not be taken into account in the percentage calculation, percentages with valid data will be presented.

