9.3 Treatment

The listing "Treatment" will include the following information:

- Center
- Patient id.
- Treatment arm (Arm A; Arm B; Arm C)
- Treatment administration (Yes/No).
 - If so, reasons will be detailed.
- Administered doses
- Treatment interruption (Yes/No).
 - If so, the reasons will be indicated.
- Pre-medication (Yes/No). If so, it will be indicated:
 - Type (antiemetic, gastric protector, antihistamine and corticosteroids)
 - Code (ATC)

- Active substance
- Dose
- Route of administration
- Units
- Days on treatment with plitidepsin
- Total dose of plitidepsin administered (sum of daily doses - mg)
- End of treatment date
- End of treatment (Treatment completed according to protocol; Withdraw informed consent; Non related adverse event; Adverse reaction to plitidepsin; Death; Investigator's decision; Administration of prohibited medication; Other).
 - If the adverse event is not related to the drug, the description of event and grade will be provided (1; 2; 3; 4; 5; Not available).
 - If the adverse event is related to the drug, the description of event and grade will be provided (1; 2; 3; 4; 5; Not available).
 - If it is Investigator's decision: specify
 - If other: specify

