9.8 End of study

The listing “End of study” will include the following information:

- Center
- Patient id.
- Treatment arm (Arm A; Arm B; Arm C)
- End of study (yes/no)
- End of study reason (Follow-up completed according to protocol; Withdrawal by subject; Lost to Follow-up; Death; the patient was randomized but did not receive the study drug; Investigator's decision; Early end of study; Other).
 - Lost to Follow-up: date.
 - The patient was randomized but did not receive the study drug: specify.
 - Investigator's decision: specify.
 - Early end of study: specify.
 - Other: specify.
- Follow-up time: defined as the time, in days, between the informed consent signing date until the end of study date by the patient. If the study has not been completed at the time of the analysis, the date of the last follow-up of the patient will be taken.

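### Under Protocol 8.1 a non-allowed treatment takes the patient out of the study, and nothing then requires the scheduled efficacy, laboratory and ECG assessments to continue

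*Protocol*

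**What the plan says.** **Withdrawal.** Protocol 8.1 opens with "Patients will be excluded or withdrawn from the study for any of the following reasons". It gives two reasons: withdrawal of consent and "Administration of treatments not allowed in the protocol". Both concern the study, not only the drug.

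**Afterwards.** Protocol 8.2 follows dosed patients who withdraw for at least 28 days after the last dose, and states the purpose as "to follow up on possible open adverse events at withdrawal". It names no efficacy, laboratory or ECG assessment.

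**Which treatments.** Protocol 9.7 says "Concomitant administration of interleukin-6 receptor inhibitors and immunomodulatory drugs is not permitted" and also bars chloroquine and its derivatives, with no end date for either. The same section lets the investigator give other COVID-19 drugs from 24 hours after the last plitidepsin dose.

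**Replacement and analysis set.** Protocol 8.3 replaces "Patients who discontinue study treatment before the end of the three proposed administrations for reasons other than" adverse events of grade 3 or higher. Protocol 12.3 and SAP 4.1 require three doses and at least two weeks of follow-up for the efficacy population. They make an exception for patients whose dosing was cut short by an unfavourable disease course.

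**Missing data.** SAP 3 states that "missing values will not be taken into account in the percentage calculation". SAP 4.6 plans no imputation.

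**Disposition in the SAP.** SAP 9.3 places prohibited medication among the end-of-treatment reasons ("Administration of prohibited medication; Other"). SAP 9.8 begins its list with "End of study reason (Follow-up completed according to protocol; Withdrawal by subject; Lost to Follow-up; Death" and does not name prohibited medication anywhere in it.

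**The concern.** The rule joins two separate events: receiving a drug outside the protocol, and ceasing to be observed. A patient is more likely to be given such a drug when the disease is getting worse. Stopping observation at that point removes patients selectively, just before the outcomes that Protocol 6.3 counts at Days 7, 15 and 31: invasive ventilation or ICU admission, non-invasive ventilation and oxygen therapy. Viral load and PCR at Days 4, 7, 15 and 31 are exposed in the same way.

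These endpoints are secondary, but Protocol 6.1 and 6.3 use efficacy together with safety to choose the dose for the next trial. Each arm ends with 15 patients, so one or two selective losses change what is reported for a dose. Laboratory changes and ECG findings belong to the primary endpoint in Protocol 6.2, and 8.2 does not require them after withdrawal either.

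**Working it through.** **1. The plan's own figure.** Three arms of 9 plus 6 give 3 × (9 + 6) = 45, or 15 per arm, as Protocol 6.1 states. The trial is descriptive, with no alpha, power, assumed event rate or dropout rate, so there is no sample-size formula to test.

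**2. What remains required after an 8.1 withdrawal.**

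| Data | Required after withdrawal? | Source |
|---|---|---|
| Death | Largely yes, as a serious adverse event to 28 days | 11.1.2, 11.3.1, 11.3.4 |
| Adverse events | Yes under 11.3.1 (all events); 8.2 names only those already open | 8.2, 11.3.1, 11.3.4 |
| Viral load, PCR | Not stated | Section 10, 8.2 |
| Laboratory tests, ECG | Not stated | Section 10, 8.2 |
| Oxygen, ventilation, ICU | Not stated as endpoints; partly through adverse event reports | 6.3, 8.2, 11.2.5 |

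Adverse event reporting cannot stand in fully for the last row. Protocol 11.2.5 keeps disease-related changes in safety parameters out of adverse event reporting unless they are more serious than expected.

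**3. When the rule can be triggered.** Dosing is on Days 1 to 3, so the 24-hour point falls on about Day 4. Up to then, other COVID-19 drugs are outside the protocol. Afterwards 9.7 permits them. Whether that permission also lifts the bar on IL-6 receptor inhibitors, immunomodulators and chloroquine is not stated. If it does not, the trigger lasts to Day 31 for those classes. The Section 10 calendar marks other COVID-19 treatments from Day 2, whereas its note 12 starts them 24 hours after the last dose.

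**4. The efficacy population.** Take a patient given all three doses, then a barred drug, then withdrawn before two weeks. The exception in 12.3 covers incomplete dosing only, so it does not apply. Whether the adverse event follow-up in 8.2 satisfies the two-week condition is not stated. This patient may therefore drop out of the efficacy analysis.

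**5. Illustration of size.** Let an arm of 15 have e true events, and let k of those patients be withdrawn before the event with the outcome never recorded. The valid-data percentage is (e − k)/(15 − k). The values of e and k are assumptions. Intervals are exact 95%.

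| e | k = 0 | k = 1 | k = 2 |
|---|---|---|---|
| 2 | 2/15 = 13.3% (1.7–40.5) | 1/14 = 7.1% (0.2–33.9) | 0/13 = 0% (0–24.7) |
| 3 | 3/15 = 20.0% (4.3–48.1) | 2/14 = 14.3% (1.8–42.8) | 1/13 = 7.7% (0.2–36.0) |

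For e from 1 to 4, the first such loss lowers the rate by about 5 to 7 percentage points. If a lost patient is replaced by one without the event, the denominator stays at 15. With e = 3 the results are then 2/15 = 13.3% and 1/15 = 6.7%.

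**6. Chance that it happens at all.** If each patient has probability q of such a withdrawal, at least one occurs in n patients with probability 1 − (1 − q)^n. For q = 2%, 5% and 10% (assumed) this is 26%, 54% and 79% in an arm of 15, and 60%, 90% and 99% among 45.

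**The case against.** **Deaths.** A reader might infer that these patients' deaths are lost. The documents do not support that. Death is a serious adverse event (11.1.2), events are recorded to 28 days after the last dose (11.3.1 and calendar note 13), and 11.3.4 extends follow-up to patients who withdraw early. Nothing says that 8.2 cuts back 11.3.1. This objection stands.

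**Rescue in general.** It is tempting to read 8.1 as removing everyone who worsens and is rescued. Most COVID-19 treatment is allowed from about Day 4 and does not trigger 8.1. This stands too. What remains is the early window and the unresolved bar in 9.7.

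**Replacement.** One might infer from 8.3 that early failures are exchanged for new patients. But 8.3 adds a patient without saying that the first one leaves the analysis. Protocol 12.3 and SAP 4.1 keep those who stopped dosing because the disease worsened, and everyone dosed stays in the safety population. Staying in a population does not, however, generate assessments that are no longer required.

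**The SAP expects these data.** SAP 9.6 lists tocilizumab and chloroquine as other treatments received, and SAP 8.1 relates PCR, ventilation and ICU results to other COVID-19 treatment. SAP 9.8 has free-text categories in which a study withdrawal could be recorded, so part of the conflict is one of labels. This is fair, but it shows that the SAP assumes continued observation that Protocol 8.1 and 8.2 do not provide.

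**Size.** The illustration is a worst case: every such patient is withdrawn before the event and the event is never recorded. No rate comes from the documents. The endpoints are secondary and descriptive, and the intervals at n = 15 are far wider than the shift. All of this limits the weight of the point. Even so, the error has a likely direction, towards fewer failures.

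**Conclusion.** The point holds in a limited form. Protocol 8.1 ends study participation for a non-allowed treatment. Protocol 8.2 does not require the scheduled viral load, PCR, laboratory, ECG, oxygen, ventilation or ICU data afterwards, and the SAP analyses only what is present. The resulting loss is probably informative for the secondary efficacy endpoints.

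The certain window is from first dose to about Day 4. Exposure to Day 31 depends on a reading of 9.7 that the documents leave open. Deaths and new adverse events to 28 days should largely be captured, although the wording of 8.2 is narrower than that of 11.3.1.

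The size is unknown. On the assumptions shown, one lost event costs an arm about 5 to 7 percentage points. A reader might also infer that the loss differs by dose, because the trial is unmasked. That is possible, but nothing in the documents shows it. This should be fixed before the data are used for dose selection. It does not undermine the primary safety analysis as a whole.

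**What to change.** **Protocol 8.1 and 8.2.** State that receiving a non-allowed treatment does not end study follow-up. Every patient who received any plitidepsin continues all scheduled assessments, the Protocol 6.3 outcomes and the recording of new adverse events to Day 31, unless consent to follow-up is itself withdrawn. Align the adverse event wording of 8.2 with 11.3.1. How plitidepsin is handled in such a patient is a separate clinical matter and is not addressed here.

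**SAP.** Keep these patients in the efficacy population and in the timed percentages, count events after the non-allowed drug, and flag the patients in the listing.

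**Passages to reconcile, without a view on which clinical rule applies:**
- Protocol 8.1 with SAP 9.3 and 9.8: end of treatment or end of study.
- The open-ended bars in Protocol 9.7 with the 24-hour permission in the same section.
- The Section 10 calendar row marked from Day 2 with its note 12.

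**Cost.** A few sentences in each document. The visits already exist, and oxygenation method is already recorded with vital signs. The drawback is that outcomes after a non-allowed drug reflect plitidepsin plus that drug, which the flag makes visible. Outcomes that were never collected cannot be recovered later.

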### **8.2. Management of withdrawals**

Patients who receive at least one dose of plitidepsin and withdraw from the study will be followed for at least 28 days after administration of the last dose of plitidepsin to follow up on possible open adverse events at withdrawal.

### **8.3. Replacement of subjects and reserve subjects**

Patients who sign the study consent and are not randomised will be replaced.

Patients who discontinue study treatment before the end of the three proposed administrations for reasons other than  $\geq$  grade 3 adverse events will be replaced.

## **9. INVESTIGATIONAL PRODUCT**

### **9.1. Description of the investigational product**

Plitidepsin is licensed in Australia for the treatment of multiple myeloma.

Safety information for plitidepsin is included in Annex 7.

#### **9.1.1. Description**

Plitidepsin is supplied as a powder for concentrate for solution for infusion at a concentration of 2 mg/vial. Before use, the vials are reconstituted with 4 ml of reconstitution solution to obtain a colourless to slightly yellowish solution containing 0.5 mg/ml of plitidepsin, 25 mg/ml of mannitol, 0.15 ml/ml of macroglycerol ricinoleate oil, 0.15 ml/ml of ethanol and 0.70 ml/ml of water for injection. An additional dilution should be made in any suitable intravenous solution prior to infusion.

#### **9.1.2. Packaging**

Plitidepsin 2 mg is supplied in a Type I clear glass vial with a bromobutyl rubber stopper covered with an aluminium seal. Each vial contains 2 mg of plitidepsin.

The solvent for the reconstitution of macroglycerol ricinoleate (polyoxyl 35 castor oil)/absolute ethanol/water for injection, 15%/15%/70% (v/v/v) is supplied in a Type I colourless glass vial. The ampoules have a volume of 4 ml.

Plitidepsin will be labelled with the study protocol code, the batch number, the content, the expiry date, the storage conditions, the name of the investigator and the sponsor. The study drug will be labelled in accordance with Annex 13 of the European Good Manufacturing Practices.

### **9.1.3. Shipping, storage and destruction**

Plitidepsin should be stored between 2°C and 8°C and the vials should be kept in the outer carton to protect them from light.

The drug in these conditions is stable for 60 months.

Any unused product or waste materials must be disposed of in accordance with local requirements for cytotoxic drugs.

### **9.2. Dosage and administration**

Patients included in the study will be randomised in a 1:1:1 ratio to receive:

- Arm A) 1.5 mg of plitidepsin administered as a 1.5-hour infusion, once a day for 3 consecutive days.
- Arm B) 2.0 mg of plitidepsin administered as a 1.5-hour infusion, once a day for 3 consecutive days.
- Arm C) 2.5 mg of plitidepsin administered as a 1.5-hour infusion, once a day for 3 consecutive days.

#### **See guidelines for medication preparation in Annex 4.**

Personnel should be trained and qualified to reconstitute and dilute the medication and should wear protective clothing including a mask, goggles and gloves during reconstitution and dilution.

Accidental contact with skin, eyes or mucous membranes should be treated immediately with large amounts of water.

All patients should receive the following prophylactic medications 20-30 minutes before the infusion of plitidepsin:

- Diphenhydramine hydrochloride 25 mg iv or equivalent.
- Ranitidine 50 mg iv or equivalent.
- Dexamethasone 8 mg intravenous.
- Ondansetron 8 mg i.v. slow infusion 15 minutes or equivalent

Ondansetron 4 mg oral will be administered every 12 hours until 48 hours after the last administration of plitidepsin.

After reconstitution of the 2 mg plitidepsin vial with 4 ml of the solution for reconstitution of macroglycerol ricinoleate/ethanol/water for injection, the reconstituted solution should be diluted and used immediately after preparation.

If not used immediately, storage times and conditions until use are the responsibility of the user.

The reconstituted concentrated solution of the drug product has been shown to be physically, chemically and microbiologically stable for 24 hours under refrigerated conditions ( $5^{\circ}\text{C}\pm 3^{\circ}\text{C}$ ) and for 6 hours when stored in the original vial under indoor light at room temperature.

If storage is required before administration, solutions should be stored refrigerated and protected from light and should be used within 24 hours after reconstitution.

### **9.3. Duration of treatment**

Patients included of the study will receive treatment for 3 days.

### **9.4. Criteria for dosage modification**

No dose reduction has been contemplated.

### **9.5. Management of infusion reactions (e.g. *hypersensitivity reaction*)**

In the event of a serious/life-threatening infusion reaction (grade  $\geq 3$ ), the plitidepsin infusion should be discontinued and immediate treatment with oxygen and bronchodilators should be considered. Treatment should be administered with diphenhydramine iv 50 mg or equivalent, hydrocortisone iv 100 mg and epinephrine (adrenaline) should be added if clinically indicated. The infusion should not be resumed and treatment with plitidepsin should be discontinued.

For mild or moderate/non-life threatening reactions (grade  $\leq 2$ ) such as allergic symptoms, the infusion should be stopped immediately and vital signs and pulse oximetry will be continuously monitored. Before resuming infusion of plitidepsin, iv dexamethasone 4 mg premedication (or equivalent) must be administered 20-30 minutes beforehand. If symptoms persist after stopping the infusion and administering dexamethasone, diphenhydramine 50 mg iv or equivalent and hydrocortisone 100 mg bolus iv or equivalent will be administered.

Symptoms and vital signs should be re-evaluated after 30 min. If they are normal or have improved, the infusion may be resumed at a third of the initial infusion rate during the first hour. Signs and symptoms should be continuously monitored during the infusion. Subsequently, the infusion rate could be increased according to tolerance. Any additional infusion will be started at a reduced infusion rate and IV prophylactic premedication will be administered as described above. The patient will be monitored during the first hour after the infusion to detect symptoms. If no hypersensitivity reactions are observed, the

infusion rate could be increased again. In any case, if symptoms do not improve after 30 minutes, anti-H1 and/or corticosteroids will be administered until resolution, and treatment with plitidepsin will be discontinued.

